## **I. Hypotheses and Specific Aims:**

**Overall Objective:** The overall goal of this application is to examine the effects of an  $\alpha 7$  nicotinic receptor partial agonist (DMXB-A) on neuronal, physiological and behavioral mechanisms of obesity. This will be accomplished by evaluating the following outcomes following approximately 12 weeks of treatment with either DMXB-A or placebo, in a randomized, double blind, parallel design study:

**Aim 1.** To determine if approximately 12 weeks of treatment with the  $\alpha 7$  nicotinic partial agonist DMXB-A, as compared to placebo, alters measures of neuronal response to a meal in overweight/obese individuals.

**Aim 2.** To determine if approximately 12 weeks of treatment with the  $\alpha 7$  nicotinic partial agonist DMXB-A, as compared to placebo, alters measures of food intake behavior, body weight and fat mass in overweight/obese individuals.

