### **IV. Research Methods**

#### **A. Outcome Measure(s):**

- a. Neuronal response to visual food cues
- b. Intrinsic resting state network activity (default network)
- c. Body weight and fat mass
- d. Appetite ratings

The primary outcome measure in this study is neuronal response, to both food cues and during rest.

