#### **C. Study Design and Research Methods**

Participants will complete two study phase assessments: (1) at baseline and (2) post-intervention.

**Study Phase Assessments:** The following evaluations will be completed during both study phases: After a 1-day run-in eucaloric diet period to ensure energy and macronutrient balance, subjects will arrive the morning after an overnight fast. Prior to each study phase assessment day, participants will wear an activity monitor for 5-7 days (ActivPal, Glasgow, Scotland), to assess any activity differences between groups. Sleep habits will be assessed via brief self-report questionnaire (Pittsburgh Sleep Quality Index; PSQI) at both assessment days to determine if group differences in sleep habits are a possible confounding variable. A blood draw will not be completed at the baseline study day, unless it has been more than 60 days since the screening day. This blood draw will measure the complete metabolic panel to reassess liver function (i.e., we will not repeat all screening blood labs, only the complete metabolic panel). On the post-intervention study day, a nurse will insert an IV for blood draws in the morning. The initial blood draw will be used to measure DMXB-A levels, lipids, complete metabolic panel, and leptin. Three more blood draws will be completed on the post-intervention study day, each of which will be used to measure DMXB-A levels. If the nurse/phlebotomist has difficulty inserting the IV, a single blood draw for lipids, complete metabolic panel, and leptin will be considered acceptable. Following the first blood draw on the post-intervention study day, subjects will take their final pill capsule, prior to completing any other study measures. The remaining three blood draws will be taken approximately 1 hour after taking the pill, 2 hours after taking the pill, and 6 hours after taking the pill. During both study days, subjects will complete assessments of body composition, food and eating-related behaviors (Three Factor Eating Questionnaire (TFEQ); Power of Food Scale; Food Craving Inventory), cognitive and mood measures (Digit Span task; Coding task; Comprehensive Trail Making Test [CTMT]; Center for Epidemiological Studies Depression Scale (CES-D); State Trait Anxiety Index [STAI]), and appetite evaluations (hunger, appetite, satiety). Following these measures, subjects will be escorted to the Brain Imaging Center for fMRI measures (visual food cue task and resting-state), which will first be performed in the fasted state, then again in the fed state (approximately 30 minutes following a breakfast meal, described below). Appetite evaluations will be performed at approximately 30, 90, 120, 150, 180, and 210 minutes post-meal. Subjects may then complete a measure of resting metabolic rate, followed by a buffet-style lunch at the Anschutz Health and Wellness Center to measure ad libitum food intake.

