
**Run-In Diet:** A 1-day eucaloric, run-in diet will be performed prior to the study day during each of the study phase assessments. The caloric value of the diet will be determined by taking into account age, gender and weight, adjusted for physical activity, and will have a macronutrient composition of approximately 50% carbohydrate, 30% fat, and 20% protein. This approach has been used effectively by our group in a number of prior studies. All meals will be prepared by the metabolic kitchen of the Anschutz Health and Wellness Center (AHWC) or the CTRC. Subjects will report to the AHWC or CTRC in the morning, be weighed, eat breakfast on the unit, and pick up food for the remaining meals (lunch, dinner, snack). Subjects will be asked to return containers and uneaten food from the previous day when they arrive the next day for the study day. Subjects will be asked to not consume any other food or beverages and to maintain usual activities.

**Resting Metabolic Rate (RMR):** After approximately 30 minutes of quiet rest, RMR may be measured prior to lunch on each study day, using standard indirect calorimetry with the ventilated hood technique (Parvo Medics Truemax 2400). It is acceptable to omit this measure if data cannot be collected in accordance with COVID-19-related University and CTRC guidelines, or if participants/staff feel it would be safer to omit it.

**Body Composition:** Body composition will be measured using BOD POD air displacement plethysmography (Life Measurement, Inc., Concord, CA) at baseline and after the intervention. This measure takes approximately 2 minutes to complete.

**Blood Analyses:** Blood analyses will take place as follows (also see study procedures table, p.7): Complete metabolic panel at screening and at weeks 4, 8 and 12. Lipid panel and leptin at screening and week 12. CBC, TSH, A1c, and cotinine at screening. At the post-intervention study day (week 12 visit), we will utilize an IV catheter to facilitate 4 separate blood draws to measure DMXB-A blood levels. These draws will take place immediately prior to morning study drug dosing, and approximately 1 hour post-dose, 2 hours post-dose and 6 hours post-dose. If the nurse/phlebotomist has difficulty inserting the IV, a single blood draw for lipids, complete metabolic panel, and leptin will be considered acceptable.

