#### **F. Data Analysis Plan:**

A mixed model repeated measures analysis of variance will be used to assess group differences (DMXB-A vs. placebo) in intervention-associated change from baseline to post-intervention. Potential covariates will include age, sex, and DMXB-A plasma level. Missing data will be considered missing at random. Missing data generally occur from subjects who cannot complete one arm of the test or from a technical failure. fMRI data will be processed with Statistical Parametric Mapping (SPM12, Wellcome Trust Centre for Neuroimaging) in Matlab. All data initially will be visually inspected for motion, field homogeneity and reconstruction errors. Data from each participant will be realigned to the first volume, normalized to the Montreal Neurological Institute (MNI) template using a gray-matter-segmented IR-EPI as an intermediate to improve registration, and smoothed with an 8-mm full width at half maximum Gaussian kernel to improve signal to noise ratio and account for the non-independence on neighboring voxels. For the visual food-cue task, after preprocessing, a 128-second high-pass filter will be applied to remove low-frequency fluctuation in the BOLD signal. To account for both intersubject and intrasubject variability, a random effects statistical model will be utilized. To generate the random effects model in SPM8, statistical parametric maps will first be generated for each subject using the general linear model to describe the variability of the data on a voxel by voxel basis. The hemodynamic response will be modeled with a double gamma function, without

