temporal derivatives. Because the first level analysis only considers a single source of error variance, in this case scan-to-scan residual error, a second level analysis will be performed to incorporate both within subject and between subject variance, thus allowing inference to the population. This will be accomplished by summarizing each individual subject's data with one parametric map (accounting for within subject variance), and then assessing these measures across subjects (accounting for between subject variance), thereby implementing a random effects model. Single subject SPM contrast images will be entered into a second-level repeated measures ANOVA in which contrasts of interest will be evaluated. For the resting state network analysis, group ICA analyses will then be performed using the GIFT toolbox (<http://icatb.sourceforge.net>). The dimensionality of the data from each subject first will be reduced using principle component analysis (PCA). Data sets will then be concatenated into an aggregate data set and the number of spatially independent sources will be estimated with a minimum description length (MDL) algorithm^66. The data will be further reduced to the number of independent components indicated by MDL. An independent component analysis (ICA) then will be performed using the infomax algorithm^67. Individual ICA maps will then be back-reconstructed. The default network component will be identified by selecting the independent component with the highest spatial correlation to a default network mask. This component will be entered into a second-level model in SPM12.

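### The missing-at-random assumption overlooks the plan's own withdrawals, an unchecked risk for the scalar outcomes; plasma level should leave the between-arm model

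*Combined protocol and SAP*

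**What the plan says.** Section IV.F compares the arms on change from baseline to post-intervention with a mixed model repeated measures ANOVA. On missing data it says "Missing data will be considered missing at random" and then "Missing data generally occur from subjects who cannot complete one arm of the test or from a technical failure". The reference to an arm of the test is ambiguous; it may mean a fasted or fed session. On covariates: "Potential covariates will include age, sex, and DMXB-A plasma level". For imaging: "Single subject SPM contrast images will be entered into a second-level repeated measures ANOVA in which contrasts of interest will be evaluated".

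Section IV.C states "Participants will complete two study phase assessments: (1) at baseline and (2) post-intervention". The Blood Analyses paragraph in section IV.D plans an IV catheter on the post-intervention day "to facilitate 4 separate blood draws to measure DMXB-A blood levels". No earlier plasma level is described. If the IV cannot be placed, a single draw without a DMXB-A level is acceptable.

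Plans to Minimize Risk (DMXB-A) removes participants for inability to attend biweekly visits, non-compliance or poor tolerability. It also removes them under liver and QT criteria, and in both cases the participant leaves the study, not only the drug. Potential Scientific Problems mentions dropouts as one reason for choosing 12 weeks, without a rate.

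The supplied text states no analysis set, no outcome collection after drug is stopped and no missing-data sensitivity analysis.

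**The concern.** Aim 2 asks whether DMXB-A "alters measures of food intake behavior, body weight and fat mass in overweight/obese individuals". Nausea is one of the two chief symptoms named in section IV.D. People who leave because of nausea may well differ in appetite, intake and weight at week 12 from people who stay. The stated causes of missing data do not cover that route.

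If leaving depends on the unseen week-12 value after allowing for arm, baseline, age and sex, the data are not missing at random for the described model. If the rate of leaving or the type of leaver also differs by arm, the estimate describes those who stayed rather than all who were randomised. The direction is not known in advance. Losing the people whose appetite was most suppressed would hide an effect on weight; losing the non-responders would exaggerate one.

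The third candidate covariate adds a separate difficulty. Plasma level is measured after randomisation, is absent for leavers and is itself a consequence of assignment.

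**Working it through.** **Inputs.** The documents give no sample size, SD, dropout rate, alpha or effect size, so there is no figure of theirs to reproduce. Every rate, gap, correlation and sample size below is an assumption. Units are SD of change, the true effect is zero unless stated, and tests are two-sided at 5%.

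**1. What the model can correct.** For a leaver the described model has arm, baseline and perhaps age and sex. In simulation with 15% vs 5% leaving:
- Leaving driven by baseline only: mixed-model bias 0.000.
- Leaving driven by change: 0.064 (baseline–post correlation 0.5) or 0.072 (correlation 0.7), against 0.083 for completers alone.

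**2. Simple arithmetic.** Let p be the share leaving and g the completer mean minus the leaver mean. Then bias = pT·gT − pC·gC (T = DMXB-A, C = placebo).

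| Leaving T / C | gT, gC | Bias |
|---|---|---|
| 20% / 20% | 1, 1 | 0.20 − 0.20 = 0 |
| 15% / 5% | 0.5, 0.5 | 0.075 − 0.025 = 0.05 |
| 15% / 5% | 1, 1 | 0.15 − 0.05 = 0.10 |
| 25% / 10% | 1, 1 | 0.25 − 0.10 = 0.15 |
| 30% / 10% | 1, 1 | 0.30 − 0.10 = 0.20 |
| 20% / 20% | 1, 0 | 0.20 − 0 = 0.20 |
| 30% / 10% | 1, 0 | 0.30 − 0 = 0.30 |

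**3. Same mechanism, unequal rates.** Suppose leaving follows a normal latent score correlated r with change, and baseline is uninformative. Then bias = r·[φ(cT)/(1−pT) − φ(cC)/(1−pC)], where φ is the normal density and c its upper-p quantile.
- 15/5%: 0.2332/0.85 − 0.1031/0.95 = 0.166. Bias is 0.033, 0.050 and 0.083 for r = 0.2, 0.3 and 0.5.
- 25/10%: 0.3178/0.75 − 0.1755/0.90 = 0.229. Bias is about 0.115 for r = 0.5.

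This gives the range of about 0.03 to 0.12. At r = 0.5 the implied gaps are 0.85 to 1.09 SD, so the upper end already assumes leavers who are quite different.

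**4. Type of leaver differs.** In a separate simulation, leaving depended on the unseen week-12 value in the drug arm only (30% vs 10%). The bias was 0.24 SD in size. The same mechanism in both arms (22% each) gave zero.

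**5. Effect on the test.** SE = √[1/(n(1−pT)) + 1/(n(1−pC))].
- n = 20 per arm at 15/5%: √(1/17 + 1/19) = 0.334, so 0.083 is 0.25 SE.
- Over n = 20 to 60, type I error is 5.7–7.1% for a bias of 0.083 and 6.2–8.8% for 0.115. For 0.033–0.050 it is about 5.1–5.8%.
- At n = 30, a bias of 0.20 (20/20%) gives 10.7% and 0.30 (30/10%) gives 17.8%.

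**6. Plasma level as covariate.** Level should be zero on placebo. With 1:1 allocation and coefficient of variation CV in the drug arm, adding level multiplies the SE of the arm effect by √(1 + 1/(2CV²)). Assumed CV 0.7 gives √2.02 = 1.4; CV 0.28 gives √7.38 = 2.7. If the drug effect is proportional to level, the arm coefficient is the effect at level zero, so the arm effect disappears from it.

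**7. What each repair recovers (15/5%, starting from 0.083).**
- Leavers give week-12 outcomes: 0.058, 0.037 or 0.017 if 25%, 50% or 75% do so, provided they resemble the other leavers in their arm.
- Weights at weeks 4 and 8 (assumed correlations 0.75, 0.6 and 0.8 between weeks 4–8, 4–12 and 8–12): 0.032 if all leave after week 8, 0.056 if all leave between weeks 4 and 8, 0.054 if leaving is evenly spread, and no gain if all leave before week 4.
- Side-effect scores as auxiliary variables: 0.079 or 0.070 at correlations of 0.3 or 0.5 with the tendency to leave.

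**The case against.** The plan's wording is not exclusive. It says what missing data generally arise from, and Potential Scientific Problems shows that dropout was considered. So the text is a thin rationale, not a denial that people leave. That stands.

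Section IV.D reports that nausea and headache have not significantly exceeded placebo rates, and that Phase 2 liver enzyme elevations were equally frequent in both arms. This makes a large difference between arms less likely. It does not test for one here.

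A reader might infer several stronger things that the documents do not support:
- **That no outcome exists between baseline and week 12.** The Blood Analyses paragraph refers to a procedures table that is not in the supplied text, and interim weights may be scheduled there. What can be said is that section IV.F analyses only baseline-to-post change.
- **That the primary result is biased.** Section IV.A says "The primary outcome measure in this study is neuronal response, to both food cues and during rest". A participant without a second scan has no post-intervention contrast image, but nothing in the documents links leaving to neuronal response.
- **That the bias is known to be modest, or known to be large.** Either depends on the assumed gap and on whether the type of leaver differs by arm.
- **That the withdrawal rules contradict each other.** They do not.

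Finally, the aims concern 12 weeks of treatment in a mechanistic trial, so off-drug data are not obviously what the trial wants as its main comparison. Suppose a 0.5 SD effect vanishes off drug and 75% of 15% leavers attend week 12. The effect is then diluted by 0.5 × 0.1125/0.9625 = 0.058 SD, close to the bias removed (0.083 − 0.017 = 0.066). That objection stands, and the fix leaves the choice of main analysis to the sponsor.

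**Conclusion.** The concern holds as a conditional risk to the scalar outcomes, of minor to moderate severity. The missing-at-random rationale leaves out withdrawal routes that the plan itself creates, and the described model cannot correct for leaving related to the week-12 value beyond arm, baseline, age and sex.

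On assumed inputs the bias is zero with equal rates and the same mechanism in both arms. It is about 0.03 to 0.12 SD at 15/5% or 25/10% with the simulated mechanism; the simple arithmetic reaches 0.20 SD with 30% vs 10% and a full 1 SD gap in both arms. It is 0.20 to 0.30 SD when leavers lie 1 SD from completers on drug but not on placebo. No bias is shown, its direction is unknown, and no claim is made about the primary imaging outcome.

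The plasma-level covariate does not depend on these assumptions. Whatever the dropout, a post-randomisation measure of exposure does not belong in the between-arm model.

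**What to change.** 1. **Remove DMXB-A plasma level from the between-arm model.** Use it only in an exposure–response analysis within the DMXB-A arm. Cost: a sentence in section IV.F.

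2. **Allow week-12 non-imaging outcomes after stopping drug.** Leave every drug-stopping rule as it is, and let consenting participants who stop drug give weight, fat mass, appetite and food intake at week 12. Report an all-randomised analysis alongside the on-treatment analysis, and have the sponsor state which one answers the aims. Off-drug MRI is not requested. Cost: a short protocol and consent amendment and modest follow-up effort, with possible dilution of the effect in the all-randomised analysis.

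3. **Use weights from the week 4 and 8 vitals visits in the weight model.** Record them if they are not already scheduled. Cost: a weighing at two existing visits. This helps only the weight outcome, and only for people who leave after week 4.

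4. **In support,** name the withdrawals in the missing-data rationale, report them by arm and reason, and add one delta-adjusted sensitivity analysis by arm for the scalar outcomes. Using the biweekly side-effect scores as auxiliary variables is optional. Its yield is low unless the scores predict leaving strongly, and anyone who leaves before week 2 has none.

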#### **G. Summarize Knowledge to be Gained:**

Obesity is a serious and growing health problem in the United States. Obesity is associated with health problems such as type 2 diabetes and cardiovascular disease, leading to substantially diminished quality of life and increased mortality. Given the health and quality-of-life effects of obesity, developing effective treatments clearly is an important goal.

